### Table 2Simulation Results for Various Scenarios

The average sample size over the 5000 clinical trials simulated under Scenarios 1-3 was 15.2, 15.5, and 15.1 respectively.

## 5.2. Part 2: Molecularly-Defined Tumor Histology Groups

Once the recommended dose(s) and schedule(s) is/are confirmed from Part 1, at least 12 and up to 30 subjects per group will be enrolled at that dose(s) in Part 2, guided by decision rules defined in the Protocol in Section 13.6.2. These guidelines are based on the predictive probabilities of success if enrollment were to continue to 30 subjects using the methodology of [Lee, 2008].

The null hypothesis is:

# $H_0: p \le 10\%$

The alternative hypothesis is:

## $H_A:p \ge 30\%$

Starting with a group of 12 subjects and allowing for a maximum sample size of 30, this design will have a type I error rate ( $\alpha$ ) of 0.15 and 94% power. Group enrollment will be stopped early for futility if the predictive probability of success is less than 6%. The trial would not stop early for success. The Bayesian Prior was Beta (0.2, 0.8), a weak prior with a mean response rate of 20%. The group outcome will be considered successful if the posterior probability of (P >0.10 | observed data) is ≥80%. The futility boundary described in the Protocol Section 13.6.2 was calculated based on the optimizing criterion of maximizing the power under the alternative hypothesis.

Under the null hypothesis, the expected sample size is 20 subjects and the probability of early termination is 77%. Under the alternative hypothesis, the expected sample size is 29 subjects and the probability of early termination is 5%.

### 5.3. Sample Size Sensitivity

No analysis of sample size sensitivity was performed.

### 5.3.1. Sample Size Re-estimation

Sample size re-estimation is not planned for this study.

# 6. ANALYSIS POPULATIONS

The **All Treated Population** is defined as all subjects who receive at least one dose of GSK2849330. Safety will be evaluated based on this analysis population.

The **PK Concentration Population** will consist of all subjects from the All Treated Population for whom at least one post-dose PK sample is obtained and analyzed. This population will be used for the concentration tables, listings, and figures.

The **PK Parameter Population** will consist of all subjects from the PK Concentration Population for whom valid and valuable pharmacokinetic parameters were derived. This population will be used in the assessment and characterization of PK parameters.

The **PD Population** will consist of all subjects from the All Treated Population and for whom at least one evaluable paired pre-treatment PD sample and on-treatment PD sample were obtained and analyzed. This population will be used in all PD tables, listings, and figures.

The **PGx Population** will consists of All treated Population subjects who have not received an allergenic bone marrow transplant, and voluntary agree to participate in the PGx analysis of the study, and refusal to participate will not indicate withdrawal from the clinical study. This population will be used in listing of PGx sampling accountability.

# 6.1. Analysis Datasets

Analysis datasets are "analysis-ready" datasets, i.e., analysis datasets that have a structure and content that allows statistical analysis to be performed with minimal programming. An analysis-ready dataset is ready to be used directly by statistical analysis software with only minimal additional processing, as sorting of the observations or the selection of the appropriate records from the analysis dataset. No complex data manipulations such as transformations or transpositions are required to perform the supported analysis.

# 7. TREATMENT COMPARISONS

With respect to primary objectives and endpoints, no formal treatment comparisons are being tested. The primary focus will be on determining the RP2D based on the safety,

efficacy, PD and PK of pharmacokinetics of GSK2849330 in subjects with advanced cancer. Most of the analysis will be descriptive or exploratory.

# 7.1. Data Display Treatment and Other Subgroup Descriptors

Treatment groups with the same dose and the same administration frequency will be combined in final analyses as displayed in the table below. All data will be summarized or listed by the treatment group except PK concentration data, which will be listed by part and dose cohort.

Treatment	Treatment Description	Treatment Label / Column Header
Code		
1	Part 1 DE Cohort: 1.4 mg/kg weekly	Part 1 Cohort: 1.4 mg/kg weekly
2	Part 1 DE Cohort: 3 mg/kg every 2 weeks	Part 1 Cohort: 3 mg/kg every 2 weeks
3	Part 1 DE & PK/PD Cohort: 10 mg/kg every 2 weeks	Part 1 Cohort: 10 mg/kg every 2 weeks
4	Part 1 DE & PK/PD Cohort: 30 mg/kg every 2 weeks	Part 1 Cohort: 30 mg/kg every 2 weeks
5	Part 1 DE & PK/PD Cohort: 30 mg/kg weekly	Part 1 Cohort: 30 mg/kg weekly
6	Part 1 PK/PD Cohort: 3 mg/kg weekly	Part 1 Cohort: 3 mg/kg weekly
7	Part 2 Expansion Cohort: 30 mg/kg	Part 2 Cohort: 30 mg/kg

# 8. GENERAL CONSIDERATIONS FOR DATA ANALYSES

Analysis datasets will be created according to IDSL standards, and data will be listed and summarized according to GSK Integrated Data Standards Library (IDSL) reporting standards. Formatting for dates, times, and decimal places will follow GSK standards except where specified.

## 8.1. Reporting Conventions

- All data are reported according to the dose/regimen initially received by the subject.
- Data will be listed by treatment group, centre ID, and subject.
- Planned times relative to investigational product dosing will be used in all summary tables and figures.
- Unscheduled visits will be included in the listing using actual time and may be used in deriving the maximum or minimum value over time (e.g. worst-case value post dose). However, unscheduled visits will not be included in summaries by planned time.

- Only pre-specified planned times will be used in the summaries, statistical analyses and calculations of any derived parameters (except for PK parameters). Unscheduled readings (lab, EGC, etc) will only be listed.
- Actual, rather than planned, sampling times will be used in the derivation of PK parameters and in the individual concentration-time plots. Planned times will be used in the descriptive summaries and in mean and median plots. Listings of PK concentration-time data will be done by actual sampling times relative to dosing time.
- No formal assessment windows will be defined for the purpose of classifying measurements obtained outside scheduled assessment times.
- Programmers should refer to GSK IDSL standards (when applicable) for decimal place conventions and expand if necessary. Unless stated otherwise, descriptive summaries will include n, mean, standard deviation (SD), median, minimum and maximum for continuous variables and n and percent for categorical variables. Display minimum and maximum in the same precision as data was collected, mean and median using 1 additional decimal place, and SD using 2 additional decimal places.
- This is a multicenter study. Data from all study sites will be integrated and no controlling for centre-effect will be considered in the statistical analyses.
- Analyses are to be performed using the SAS System, Version 9.3 or higher. Programs will be imported into HARP and the final output will be produced by running drivers in HARP. Some graphics may be produced using the TSCG (Tibco Spotfire Clinical Graphics) - comprising of S-Plus (R) 7.0.6 or higher.
- Deviations from the analyses in the RAP will be identified in the final CSR.

# 9. DATA HANDLING CONVENTIONS

### 9.1. **Premature Withdrawal and Missing Data**

All subjects who withdraw prematurely from the study or investigational drug will be documented with the reason for their withdrawal recorded in the final Clinical Pharmacology Study Report (CPSR). All available data from subjects who withdraw will be listed and all available planned data will be included in the summaries according to the populations defined in Section 6.

In the event that the study is prematurely discontinued, all available data will be listed and a review will be carried out by the study team to assess which statistical analyses are still considered appropriate.

Missing data occurs when any requested data are not provided, leading to blank fields on the collection instrument. Those data will be indicated by the use of a "blank" in subject listing displays. Answers such as "Not applicable" and "Not evaluable" are not considered to be missing data and should be displayed as such.

Because the length of treatment for each subject will depend on the efficacy and toxicity of the treatment, the duration of treatment will vary across subjects. Similarly the duration of follow up will also vary. All available safety, and efficacy data will be analyzed using suitable statistical methods; subjects with shorter treatment and follow-up due to the natural history of their disease or medical necessities of the treatment of their disease will not be considered to have missing data. For endpoints which determine the percentage of responders, subjects with unknown/not evaluable or missing best overall response will be assumed to be non-responders, and will be included in the denominator when calculating the percentages.

Subjects with the designation of treatment relationship for adverse events (AE)s and serious adverse events (SAEs) missing will have the worst case assumed to impute the relationship: if relationship to study treatment is missing it will be assumed to be "Yes". There will be no other imputation for missing data other than what's described in Section 9.2 for partial dates and for missing exposure end dates.

## 9.2. Derived and Transformed Data

The following sections provide a general description of the derived and transformed variables used to describe and analyze the data. Separate analysis dataset specifications provide full details on all data derivations and transformations including descriptions of core standard algorithms and standard Oncology algorithms. The analysis dataset specifications will clearly communicate the content and source of the datasets supporting the statistical analyses.

#### 9.2.1. Reference dates

The following reference dates will be used:

- Data of Screening: for Age. Because age is an eligibility requirement.
- Treatment Start Date: for safety. Will be used to calculate study day for safety measures.
- Treatment Start Date: for efficacy. Will be used to calculate study day for efficacy measures and baseline characteristics (such as time since initial diagnosis), as well as efficacy durations.

### 9.2.2. Study Day for Safety Measures

If the date of interest occurs on or after the safety reference date then the safety study day will be calculated as (date of interest - safety reference date) + 1. If the date of interest occurs before the safety reference date then the safety study day will be calculated as (date of interest – safety reference date). There is no safety study day 0.

### 9.2.3. Study Day for Efficacy

If the date of interest occurs on or after the efficacy reference date then efficacy study day will be calculated as (date of interest - efficacy reference date) + 1. If the date of interest

occurs prior to the efficacy reference date then efficacy study day will be calculated as (date of interest – efficacy reference date). There is no efficacy study day 0.

### 9.2.4. Duration and Elapsed Time

Durations (e.g., the duration of an adverse event, duration of exposure, etc.) are calculated as the stop date minus the start date plus one.

For elapsed time (e.g., the time since initial diagnosis):

- If the reference date is on or after the event date, then the elapsed time is the reference date minus the event date + 1.
- If the reference date is before the event date then the elapsed time is the reference date minus the event date.

For converting all other durations (e.g., duration of adverse events, duration of exposure, age) to weeks, months or years use the following:

- To report the duration in weeks divide the number of days by 7.
- To report the duration in months use:

(YEAR(stopdate + 1) - YEAR(startdate)) \* 12 + (MONTH(stopdate + 1) - month(startdate) - 1) + (DAY(stopdate + 1) > = DAY(startdate))

• To report the duration in years use:

intck('year', startdate, stopdate + 1) - (month(stopdate + 1) < month(startdate) or (month(stopdate + 1) = month(startdate) and day(stopdate + 1) < day(startdate))))

The algorithms above for age and duration return whole numbers for months and years, accurately accounting for the actual numbers of days in the months or years between the start date and the stop date.

## 9.2.5. Imputation of Partial Dates

Imputed partial dates will not be used to derive study day, duration (e.g., duration of adverse events), or elapsed time variables.

Imputed dates will not be displayed in listings. However, where necessary, display macros may impute dates as temporary variables for the purpose of sorting data in listings only. In addition partial dates may be imputed for 'slotting' data to study time periods (see Section 9.3) or for specific analysis purposes as outlined below.

The partial date imputation will follow ADaM conventions. The ADaM approach is to populate the numeric date variables with the imputed date and add a flag variable to the dataset that indicates the level of imputation.

The flag variable can contain the values: blank, 'D', 'M', 'Y'.

blank: indicates that no imputation was done

D='Day': indicates that the day portion of the date is imputed

M='Month': indicates that the month and day portions of the date are imputed

Y='Year': indicates that the entire date (year, month, and day) is imputed

Example of Date Variables:

XYZD\_ - character date variable

XYZDT - numeric date variable

XYZDTFL - flag variable

Details on imputing partial dates for specific datasets are outlined below.

#### Adverse Events (AE):

Imputations in the adverse events dataset are used for slotting events to the appropriate study time periods and for sorting in data listings.

Dataset	Date	Missing Element	Rule
Adverse Events (AE)	Start Date	day, month, and year	• No Imputation for completely missing dates
		day, month	
 
If study treatment start date is missing (i.e. subject did not start study treatment), then set start date = January 1.
 
Else if study treatment start date is not missing: 
 
If year of start date = year of study treatment start date then
 
If stop date contains a full date and stop date is earlier than study treatment start date then set start date then set start date = January 1.
 
Else set start date = study treatment start date.
 
Else set start date = January 1.
 
 
 

Dataset	Date	Missing Element	Rule
		day	
 
If study treatment start date is missing (i.e. subject did not start study treatment), then set start date = 1st of month.
 
Else if study treatment start date is not missing: 
 
If month and year of start date = month and year of study treatment start date then
 
If stop date contains a full date and stop date is earlier than study treatment start date then set start date= 1st of month.
 
Else set start date = study treatment start date.
 
Else set start date = 1st of month.
 
 
 

	End Date		• No imputation for partial end dates will be performed

#### 9.2.6. Baseline Definition

Baseline will be defined as the most recent, non-missing value prior to or on the first study treatment dose date. For laboratory data, baseline will be defined as the most recent, non-missing value from a central laboratory prior to or on the first study treatment dose date. If there are no central labs collected for a subject and lab test prior to or on the first dose of study treatment, the most recent, non-missing value from a local laboratory prior to or on the first dose of study treatment will be defined as the baseline value.

For subjects who did not receive study treatment during the study, baseline will be defined as the latest, non-missing collected value.

Parameter	Baseline Days Collected		Baseline To Be Used in Analysis
	Screening	Day 1 Pre-dose	/ Summaries
Laboratory	Х	Х	Day 1 Pre-dose
Vital Signs	Х	Х	Day 1 Pre-dose
ECG	Х	Х	Day 1 Pre-dose

#### 9.2.7. Change from baseline

Change from baseline will be presented for safety data as described in Section 19.

Change from baseline is calculated as:

• For records occurring after baseline: (visit value) – baseline value.

Percent change from baseline is calculated as:

• For records occurring after baseline: ((change from baseline) / baseline value) \* 100

If either the baseline or visit value is missing, the change from baseline and/or percent change from baseline is set to missing as well.

### 9.2.8. Multiple Assessments

All data will be reported according to the nominal visit date for which it was reported (that is, no visit windows will be applied during dataset creation). Unscheduled data will only be included in the display sections that report worst- case post-baseline. For summaries that collapse data across multiple planned time intervals, mean data will be selected at each collapsed interval.

If multiple assessments on different days are reported for the same scheduled assessment, then the latest assessment for that scheduled assessment will be analyzed.

If multiple assessments are reported on the same date for the same scheduled planned time, then the mean of multiple measurements reported for the same date will be analyzed, with the exception of laboratory data reported from both central and local laboratories. If laboratory data is reported from both central and local laboratories with the same date, then the central laboratory data will be analyzed to provide consistency with measurements from other subjects. For example, for ECG data where 3 assessments are collected for each scheduled planned time, the first 3 measures will be used to compute the mean values for ECG intervals at each scheduled planned time.

Data from all assessments (scheduled and unscheduled), including multiple assessments, will be included in listings.

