7.3.6. Laboratory Assessments

All protocol required laboratory assessments, as defined in Table 13), should be performed according to the Time and Events Tables (Section 7.1). Details for the preparation and shipment of samples will be provided in the SPM.

At the discretion of the investigator, additional laboratory samples may be taken as clinically necessary. If additional non-protocol specified laboratory assessments are performed at the institution's local laboratory and result in a change in subject management or are considered clinically significant by the investigator (for example SAE or AE or dose modification) the results must be recorded in the subject's eCRF.

All abnormal laboratory tests with values that are clinically significant during study participation or within 28 days after the last dose of study treatment should be repeated until the values return to within normal range or baseline or the subject starts subsequent treatment. All subjects who have a Grade 3 or 4 laboratory abnormality at time of study withdrawal must be followed until resolution to Grade 2 or less, unless it is unlikely to improve due to underlying disease or subsequent therapy.

Hematology, clinical chemistry, urinalysis and additional parameters to be tested are listed below:

Table 13 List of Clinical Laboratory Tests

Hematology			
Platelet Count		RBC Indices:	Automated WBC Differential:
Red blood cell (RBC) Count		Mean corpuscular volume (MCV)	Neutrophils
White blood cell (WBC) Count (absolute)		Mean corpuscular hemoglobin (MCH)	Lymphocytes
Reticulocyte Count		Mean corpuscular hemoglobin concentration (MCHC)	Monocytes
Hemoglobin			Eosinophils
Hematocrit			Basophils
Clinical Chemistry			
Blood urea nitrogen (BUN) or urea	Potassium	AST	Total and direct bilirubin
Creatinine	Chloride	ALT	Uric Acid
Glucose, fasting	Total carbon dioxide (CO ₂)	Gamma glutamyl transferase (GGT)	Albumin
Sodium	Calcium	Alkaline phosphatase	Total Protein
Magnesium	Phosphate		
Routine Urinalysis			
Specific gravity			
pH, glucose, protein, blood and ketones by dipstick			
Microscopic examination (if blood or protein is abnormal)			
Other tests			
PT, INR, PTT			
Testosterone (male subjects only)			
Luteinizing Hormone (LH) (male subjects only)			
Follicle stimulating hormone (FSH) and estradiol (as needed in women of non-child bearing potential only)			

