# 12.7. Clinical Laboratory Evaluations

The assessment of laboratory toxicities will examine the following laboratory tests:

Hematology				
Platelet Count		RBC Indices:	Automated WBC Differential:	
Red blood cell (RBC) Count		Mean corpuscular volume (MCV)	Neutrophils	
White blood cell (WBC) Count (absolute)		Mean corpuscular hemoglobin (MCH)	Lymphocytes	
Reticulocyte Count		Mean corpuscular hemoglobin concentration (MCHC)	Monocyte	es
Hemoglobin			Eosinoph	ils
Hematocrit			Basophils	6
Clinical Chemistry				
Blood urea nitrogen (BUN) or urea	Potassium	AST		Total and direct bilirubin
Creatinine	Chloride	ALT		Uric Acid
Glucose, fasting	Total carbon dioxide (CO 2 )	Gamma glutamyl tra (GGT)	nsferase	Albumin
Sodium	Calcium	Alkaline phosphatas	е	Total Protein
Magnesium	Phosphate			
Routine Urinalysis				
Specific gravity				
pH, glucose, protein	i, blood and keto	ones by dipstick		
Microscopic examinat	tion (if blood or pr	otein is abnormal)		
Other tests				
PT, INR, PTT				
Testosterone (male si	• • /			
Luteinizing Hormone		• •		
Follicle stimulating ho	rmone (FSH) and	l estradiol (as needed ir	n women of	non-child bearing potential only)

Summaries of change from baseline for clinical chemistry and haematology data by maximum toxicity grade will be provided by scheduled visits for all the lab tests that are gradable by CTCAE v4.0. Number and percentage of subjects with any post-baseline

grade increase or any maximum increase to grade 3 or grade 4 will be displayed in the table. Data collected in unscheduled visits will be included in the summary of worst case on therapy category. Data with missing baseline grade will be excluded from the summary.

Another set of tables of summary of change from baseline for lab data with respect to normal range will be generated. Decreases to low, changes to normal or no changes from baseline, and increases to high will be summarized at each scheduled visit as well as for the worst case post-baseline. If a subject has a decrease to low and an increase to high during the same time interval, then the subject is counted in both the "Decrease to Low" categories and the "Increase to High" categories. In addition, the summary will include worst case changes from baseline with respect to normal range including non-scheduled visits.

Laboratory data of clinical chemistry, haematology, urinalysis, coagulation and other data will be listed for all subjects, respectively.

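### When a repeat test is filed under the same visit, SAP 9.2.8 can replace an abnormal laboratory or LVEF value with a later, usually improved one, and the SAP does not say that the superseded value still counts as worst case

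*SAP*

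**What the plan says.** **Which record is analysed.** SAP 9.2.8 applies no visit windows: "All data will be reported according to the nominal visit date for which it was reported". Where one scheduled assessment has results from several days, "If multiple assessments on different days are reported for the same scheduled assessment, then the latest assessment for that scheduled assessment will be analyzed". No exception is made for abnormal values or for worst-case displays. Several results on the same date are averaged. All assessments go into the listings.

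**What triggers a repeat.** Protocol 7.3.6 covers "All abnormal laboratory tests with values that are clinically significant during study participation or within 28 days after the last dose of study treatment" and says that these "should be repeated until the values return to within normal range or baseline or the subject starts subsequent treatment". Protocol 3.8.1.1 has raised liver chemistries monitored weekly or twice weekly until they resolve, stabilise or return to baseline. Protocol 3.8.3.1 repeats LVEF within 1 week of a qualifying fall, then every 1 to 2 weeks for 4 weeks or until recovery.

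**How unscheduled results are used.** SAP 9.2.8: "Unscheduled data will only be included in the display sections" that report worst case after baseline. SAP 12.7, on laboratory grades: "Data collected in unscheduled visits will be included in the summary of worst case on therapy category". SAP 8.1 says that "unscheduled visits will not be included in summaries by planned time" and allows such visits in deriving maxima and minima over time. A later item in the same list in 8.1 reads: "Unscheduled readings (lab, EGC, etc) will only be listed".

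**What the protocol asks for.** Section 13.7.2 wants serial safety endpoints summarised by nominal visit and also as a worst case over every on-treatment time point.

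**The concern.** Here a repeat is taken because the first value was bad, and it tends to stop when the value is good again. A rule that keeps the last value in such a series selects on the outcome, and it does so in one direction, towards less toxicity.

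Changes in laboratory values are part of the primary endpoint in both parts. SAP 12.7 tabulates subjects with any grade increase and with an increase to Grade 3 or 4, by visit and as worst case. SAP 12.8 does the same for categories of LVEF change. If the abnormal value gives way to its repeat, these tables understate toxicity, and by how much depends on how sites label repeat visits. Neither document specifies that labelling.

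**Working it through.** The plan states no figure that depends on this rule, so there is nothing to reproduce. The check applies the rules to one subject, then sizes the effect.

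**1. One subject (assumed values).** On an every-2-week schedule, the scheduled Day 29 value is Grade 3, repeats are Grade 1 on Day 32 and Grade 0 on Day 36, and the next scheduled value, Day 43, is Grade 0.

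| How the repeats are filed | Day 29 row | Worst case |
|---|---|---|
| As unscheduled | Grade 3 | Grade 3 |
| Under Day 29, superseded value kept for worst case | Grade 0 | Grade 3 |
| Under Day 29, superseded value dropped | Grade 0 | Grade 0 |

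With unscheduled filing nothing is replaced. With same-visit filing the Day 29 row changes under the stated rule, and the SAP does not say which of the last two lines applies to worst case.

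**2. The line in 8.1.** Suppose instead that the scheduled value is Grade 2 and an unscheduled repeat is Grade 3 (assumed). Under 9.2.8 and 12.7 the worst case is max(2, 3) = Grade 3. If unscheduled readings are only listed, it is Grade 2. The two instructions give different tables from the same data.

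**3. Dependence on filing.** Let n subjects have a Grade 3 or higher value at a visit, q be the share whose repeats are filed under that visit, and r be the share of those whose last repeat is below Grade 3. The expected number still shown in the visit row is n(1 − q·r). The documents give neither q nor r, so both are assumptions. For n = 10:

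| q | r = 0.5 | r = 0.8 | r = 1 |
|---|---|---|---|
| 0 | 10 | 10 | 10 |
| 0.25 | 8.75 | 8.0 | 7.5 |
| 0.5 | 7.5 | 6.0 | 5.0 |
| 1 | 5.0 | 2.0 | 0 |

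**4. Size of one lost event.**
- Part 1: protocol Table 3 plans at least 3 dose-escalation subjects and up to 3 PK/PD subjects per level from Cohort 2. SAP 7.1 combines groups with the same dose and frequency. A column of 3 to 6 subjects gives 1/3 = 33 to 1/6 = 17 percentage points.
- Part 2: SAP 7.1 shows a single pooled column. Protocol 5.1 plans about 120 subjects, so 1/120 = 0.8 points. With the minimum of 12 in each of four groups, 1/48 = 2.1 points. SAP 11 refers to early stopping of the study, so the actual column may be smaller; its size is not given.

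**The case against.** The strongest objection is that replacement needs a filing convention that the documents do not state. Protocol 7.3 speaks of additional, unplanned safety assessments. If triggered repeats count as such, they are unscheduled, stay out of the by-visit rows and feed the worst-case rows, and the abnormal scheduled value is safe. This stands: the loss is conditional on labelling. It does not remove the point, because 9.2.8 itself provides for different-day results under one scheduled assessment and then picks the last.

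A reader might infer several stronger claims. The documents do not support them:

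- *The value kept is always the recovered one.* Laboratory repeats can also end when subsequent treatment starts, liver monitoring can end at stabilisation, and LVEF repeats can end after 4 weeks. Under protocol 7.3.6 a Grade 3 or 4 laboratory abnormality at withdrawal need only reach Grade 2. Usually improved is as far as the text goes.
- *The abnormal value drops out of the worst-case tables.* No sentence says so. The SAP is silent, and protocol 13.7.2 points the other way.
- *The event survives only in listings.* Protocol 8.3 has clinically significant abnormalities, and results that lead to an intervention, recorded as adverse events, with an exception for disease-related findings. SAP 12.2 tabulates these by maximum grade. A marked ALT rise would also meet the liver stopping criteria in protocol 3.8.1 and so generate liver event records, which SAP 12.8 displays.
- *ECG is affected in the same way.* Under protocol 7.3.4, triggered ECG repeats are taken about 5 to 15 minutes apart. They share a date and are averaged under 9.2.8, so the rule on different days does not touch them.

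**Conclusion.** The concern holds in conditional form. SAP 9.2.8 is an explicit rule. Whenever it acts on a repeat triggered by an abnormal result, it favours the later and usually better value. This requires the repeat to carry the same nominal visit as the abnormal value, and how often that happens cannot be read from the documents. Loss from the by-visit laboratory and LVEF rows then follows from the text. Loss from the worst-case rows is an open question that the SAP should have closed. The conflict between the line in 8.1 and sections 9.2.8 and 12.7 is a plain contradiction that depends on no assumption about filing.

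The effect is limited to laboratory and LVEF summary tables. It is material per event in the small Part 1 columns and minor in the Part 2 column at its planned size. A reader should not conclude that toxicity would be hidden from the study report.

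**What to change.** Three changes to the SAP text:

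1. In 9.2.8, state that worst-case and maximum-grade derivations use every on-treatment value, whether scheduled, repeat or unscheduled, before any record is selected for by-visit display.
2. For by-visit rows, either class triggered repeats as unscheduled or analyse the first non-missing value in place of the latest.
3. In 8.1, delete the line that confines unscheduled readings to listings, or reconcile it with 9.2.8 and 12.7. This has to accompany the second change: if repeats are classed as unscheduled while that line stands, a peak seen at a repeat would appear in no summary.

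The cost is a few sentences and a small change to the dataset specification, with no new data. The downside is that a first value later shown to be a laboratory error would stay in the by-visit row.
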